Appendix 2 - Planned analyses

1 Baseline

Descriptive statistics:

For eligible children visited by a study nurse within 72 hours after birth, we will describe reasons for exclusion by group allocation.

Distribution of background factors will be presented by group allocation overall and by sex and region. Background factors will be summarised by counts (percentages), means (standard deviation) or medians (interquartile range) as appropriate. Information on the proportion with missing information will be provided.

Table 1: Summary of background factors by intervention and control group

• Sex• Age at enrolment• Region• Weight at enrolment• Temperature• Mid-upper-arm circumference• Head circumference• Place of birth• Socioeconomic factors (maternal education and housing conditions)

2 Primary analysis of primary outcome

The primary analysis of early infant non-accidental mortality will be assessed on a per-protocol (PP) analysis allowing for different baseline hazards according to factors used in the randomization (Region, pre-study mortality level (high/low)) and sex, thus allowing different baseline hazards for boys and girls. To account for clustering we will employ cluster-robust variance estimates.

For the primary outcome, we will use Cox proportional hazards models that allow different baseline hazards according to the above mentioned factors and with age as underlying time-scale. Deaths due to accidents will be censored.

The primary analysis of the primary outcome is described in more detail in table 2.

Table 2: Primary analysis of primary outcome

Population	Children visited within 72 hours after birth are eligible for the study. Exclusion criteria:
------------	---

	
 - Children already BCG vaccinated - Moribund children (Expected not to survive the next 24 hours, as evaluated by the health facility nurse at the enrolment visit) - Children in rural villages where the BHP mobile teams coincidentally were in the village the same day (and vaccinated all children)
Observation period	
From: Enrolment visit or 24 hours after birth, whichever comes last
 
To: 60 days of life
 
Censoring, first of:
 
 - Visit by the BHP - 60 days - Death due to accident - Date of registering first non-trial vaccine given after enrolment - Migration (migration out of the study area as per HDSS definition)
Time scale	Age
Failure definition	Death
Statistical tool	Cox proportional hazards model
Stratification	We will employ models that allow for different baseline hazards according to sex, region and pre-study mortality level
Clustering	We will use robust standard errors to account for clustering within village cluster
Outline stata code For analysis: For model checking:	<pre> stset outdate, f(dead==1) enter (max(dob+1, date_enrol) /// exit (min (dnasc+60, date_mobileteam) origin(dob) stcox random, strata(sex reg prmorlev) vce(cl regam) estat phtest, detail† stphplot, strata(random) adj(sex reg prmorlev) stcox random, strata(sex reg prmorlev) vce(cl regam) tvc(random) texp(_t) *reg=region, prmorlev=pre-study mortality level, regam=village cluster </pre>

† If the proportional hazards assumption is not fulfilled we will still report the marginal hazard ratio but it will be supplemented by hazard ratios for two-three categorized time periods.

3 Effect-modifier analyses of primary outcome

We will assess whether the effect of the intervention on the primary effect measure is modified by the following potential effect modifiers.

Table 3. Sex as a potential effect modifier of the primary outcome

Potential effect modifier	Sex
Design	We will perform the analysis as describe above (for the primary analysis) allowing the effect of the intervention to differ between the sexes.
Reasoning	Previous studies have found sex-differential non-specific effects ^{1 2} , therefore, we will assess the sex-differential effects.
Outline stata code: For analysis: For model checking:	<pre>stcox random#sex sex, strata(sex reg pmorlev) vce(cl regam) contrast random#sex estat phtest, detail† stphplot, strata(random_sex) adj(sex reg pmorlev) stcox random#sex sex, strata(sex reg pmorlev) vce(cl regam) /// tvc(random#sex sex) texp(_t) *reg=region, pmorlev=pre-study mortality level, regam=village cluster, random_sex=a four-level variable based on the four possible combinations of random and sex</pre>

† If the proportional hazards assumption is not fulfilled we will still report the marginal hazard ratio but it will be supplemented by hazard ratios for two-three categorized time periods.

Table 4. Maternal BCG scar as a potential effect modifier of the primary outcome

Potential effect modifier	Maternal BCG scar (yes/no)
Design	We will perform the analysis as described above (for the primary analysis) allowing the effect of the intervention to differ by maternal BCG-scar status
Reasoning	A recent randomized trial in Denmark found that the effect of BCG varied by whether the mother had received BCG or not ³ . Since, BCG scar is a life-long marker of a successful BCG-vaccination, we will assess whether the effect of BCG differs by maternal BCG-scar status
Outline stata code: For analysis:	<pre>stcox random#mBCGscar mBCGscar, strata(sex reg pmorlev) vce(cl regam)</pre>

For model checking:	<pre>contrast random#mBCGscar</pre> <pre>estat phtest, detail†</pre> <pre>stphplot, strata(random_mBCGscar) adj(sex reg prmorlev)</pre> <pre>stcox random#mBCGscar mBCGscar, strata(sex reg prmorlev) ///</pre> <pre>vce(cl regam) tvc(random#mBCGscar mBCGscar) texp(_t)</pre> 
* mBCGscar= maternal BCG scar, reg=region, prmorlev=pre-study mortality level, regam=village cluster, random_mBCGscar=a four-level variable based on the four possible combinations of random and maternal BCG scar

---------------------	--

† If the proportional hazards assumption is not fulfilled we will still report the marginal hazard ratio but it will be supplemented by hazard ratios for two-three categorized time periods.

Table 5. Low birthweight as a potential effect modifier of the primary outcome

Potential effect modifier	Low birthweight (<2500g: yes/no)
Design	We will perform the analysis as described above (for the primary analysis) allowing the effect of the intervention to differ by birthweight strata
Reasoning	Birthweight is an important risk factor for mortality. Previous randomised trials from Guinea-Bissau assessing the effect of BCG on mortality have been performed among low-birth-weight children.
Outline stata code: For analysis: For model checking:	<pre>stcox random#LBW LBW, strata(sex reg prmorlev) vce(cl regam)</pre> <pre>contrast random#LBW</pre> <pre>estat phtest, detail†</pre> <pre>stphplot, strata(random_LBW) adj(sex reg prmorlev)</pre> <pre>stcox random#LBW LBW, strata(sex reg prmorlev) vce(cl regam) ///</pre> <pre>tvc(random#LBW LBW) texp(_t)</pre> 
* LBW=Low birthweight, reg=region, prmorlev=pre-study mortality level, regam=village cluster, random_LBW=a four-level variable based on the four possible combinations of random and low birthweight

† If the proportional hazards assumption is not fulfilled we will still report the marginal hazard ratio but it will be supplemented by hazard ratios for two-three categorized time periods.

Table 6. Season as a potential effect modifier of the primary outcome

Potential effect modifier	Season of birth (Dry: December-May/Rainy: June-November)
Design	We will perform the analysis as described above (for the primary analysis) allowing the effect of the intervention to differ by season of birth
Reasoning	Previous studies have found that the effect of some vaccines is stronger in the dry season ⁴ . Therefore, we would like to assess if the effect of BCG and OPV differs according to season.
Outline stata code: For analysis: For model checking:	<pre>stcox random#season season, strata(sex reg prmorlev) vce(cl regam) contrast random#season</pre> <pre>estat phtest, detail† stphplot, strata(random_season) adj(sex reg prmorlev) stcox random#season season, strata(sex reg prmorlev) vce(cl regam) /// tvc(random#season season) texp(_t)</pre> 
*reg=region, prmorlev=pre-study mortality level, regam=village cluster, random_season=a four-level variable based on the four possible combinations of random and season

† If the proportional hazards assumption is not fulfilled we will still report the marginal hazard ratio but it will be supplemented by hazard ratios for two-three categorized time periods.

4 Primary analyses of secondary outcomes

Non-accident morbidity

Since it can be difficult to distinguish between hospital admissions and outpatient contact through interviews, we have defined hospital admissions as an overnight stay in a health facility. Hospital admissions due to accidents are ignored but the follow-up time is (interval) censored while the child is admitted.

Table 7: Non-accident hospitalisation

Population	Identical to primary analysis of primary outcome
Observation period	From: Enrolment visit or 24 hours after birth, whichever comes last To: 60 days of life Censoring, first of: 
 - Visit by the BHP - Date of registering first non-trial vaccine given after enrolment - Death - Hospital admission due to accident

	
 - 60 days - Migration (migration out of the study area as per HDSS definition)
Time scale	Age
Failure definition	First hospital admission – only overnight hospitalisations or arrival at the hospital and death within the first day will be considered in this analysis.
Statistical tool	Cox proportional hazards model
Stratification	We will employ models that allow for different baseline hazards according to sex, region and pre-study mortality level
Clustering	We will use robust standard errors to account for clustering within village cluster
Outline stata code For analysis: For model checking:	<pre>stset outdate, f(hosp==1) enter (max(dob+1, date_enrol) /// exit (min (dnasc+60, date_mobileteam) origin(dob) stcox random, strata(sex reg prmorlev) vce(cl regam) estat phtest, detail† stphplot, strata(random) adj(sex reg prmorlev) stcox random, strata(sex reg prmorlev) vce(cl regam) tvc(random) texp(_t) *reg=region, prmorlev=pre-study mortality level, regam=village cluster</pre>

† If the proportional hazards assumption is not fulfilled we will still report the marginal hazard ratio but it will be supplemented by hazard ratios for two-three categorized time periods.

Severe morbidity

We will evaluate the effect on severe morbidity considered as the composite outcome of non-accidental death and non-accidental hospital admission. Since it can be difficult to distinguish between hospital admissions and outpatient contact through interviews, we have defined hospital admissions as an overnight stay in a health facility. Hospital admissions due to accidents are ignored but the follow-up time is (interval) censored while the child is admitted. The potential effect modifiers for the primary outcome specified in tables 3-6 will also be assessed for the composite outcome.

Table 8: Severe morbidity

Population	Identical to primary analysis of primary outcome
Observation period	From: Enrolment visit or 24 hours after birth, whichever comes last

	To: 60 days of life Censoring, first of: 
 - Visit by the BHP - Date of registering first non-trial vaccine given after enrolment - Death/Hospital admission due to accident - 60 days - Migration (migration out of the study area as per HDSS definition)
Time scale	Age
Failure definition	Death or first hospital admission
Statistical tool	Cox proportional hazards model
Stratification	We will employ models that allow for different baseline hazards according to sex, region and pre-study mortality level
Clustering	We will use robust standard errors to account for clustering within village cluster
Outline stata code: For analysis For model checking	<pre> stset outdate, f(event==1) enter (max(dob+1, date_enrol) /// exit (min (dnasc+60, date_mobileteam) origin(dob) stcox random, strata(sex reg prmorlev) vce(cl regam) estat phtest, detail† stphplot, strata(random) adj(sex reg prmorlev) stcox random, strata(sex reg prmorlev) vce(cl regam) tvc(random) texp(_t) *reg=region, prmorlev=pre-study mortality level, regam=village cluster </pre>

† If the proportional hazards assumption is not fulfilled we will still report the marginal hazard ratio but it will be supplemented by hazard ratios for two-three categorized time periods.

Table 9: All-cause consultations

Population	Identical to primary analysis of primary outcome
Observation period	From: Enrolment visit or 24 hours after birth, whichever comes last To: 60 days of life Censoring, first of: 
 - Visit by the BHP - Date of registering first non-trial vaccine given after enrolment - 60 days

	
 - Migration (migration out of the study area as per HDSS definition) - Death - End of study
Failure definition	An out-patient consultation within the observation period
Statistical tool	Log-binomial regression
Adjustment	We will adjust the analysis for sex, region and pre-study mortality level
Clustering	We will use robust standard errors to account for clustering within village cluster
Stata code	Binreg cons random sex b1.reg pmorlev, rr vce(cl regam) *cons=out-patient consultation, reg=Region, pmorlev=Pre-study mortality level, regam=village cluster

Growth

Table 10: Mid-upper-arm circumference (MUAC)

Population	Identical to primary analysis of primary outcome
Observation time point	First visit by the mobile teams
Growth measures	MUAC will be analysed using the measured value
Statistical tool	Linear regression
Adjustment	We will adjust the analysis for MUAC at enrolment, age at MUAC measurement, sex, region and pre-study mortality level
Clustering	We will use robust standard errors to account for clustering within village cluster
Stata code	Regress MUAC random sex b1.reg pmorlev MUACenrol MUACage, /// vce(cl regam) *reg=region, pmorlev=pre-study mortality level, MUACenrol=MUAC at enrolment, MUACage= age at MUAC assessment, regam=village cluster

Table 11: Weight-for-age z-score

Population	Identical to primary analysis of primary outcome
Observation time point	First visit by the mobile teams
Growth measures	Weight will be analysed using the WHO weight-for-age z-score
Statistical tool	Linear regression
Adjustment	We will adjust the analysis for weight-for-age at enrolment, sex, region and pre-study mortality level
Clustering	We will use robust standard errors to account for clustering within village cluster

Stata code	Regress w-z-score random w-z-enrol sex b1.reg prmorlev, vce(cl regam) *w-z-score=weight-for-age z-score at first visit by the mobile teams, w-z-enrol=weight-for-age z-score at enrolment, reg=region, prmorlev=pre-study mortality level, regam=village cluster
------------	---

BCG scarring

Table 12: BCG scarring

Population	Identical to primary analysis of primary outcome
Observation timepoint	First visit after 6 months of age
Failure definition	Scar (yes/no)
Statistical tool	Log-binominal regression
Adjustment	We will adjust the analysis for sex, region and pre-study mortality level
Clustering	We will use robust standard errors to account for clustering within village cluster
Stata code	Binreg scar random sex b1.reg prmorlev, rr vce(cl regam) *reg=region, prmorlev=pre-study mortality level, regam=village cluster

Cost-effectiveness of providing BCG and OPV at birth

A cost effectiveness analysis seeking to measure the cost per death averted using a societal perspective will be performed, contrasting the costs of vaccine provision in the present programme and an outreach system as tested in the trial. The costs/savings associated with different rates of consultations and admissions will also be taken into account.

Suppurative lymphadenitis

We will assess the incidence of suppurative lymphadenitis as a reaction to BCG vaccination in the intervention and control clusters. Other serious adverse events to the BCG and OPV vaccine will be captured through the outcome measures (mortality, hospital admission and consultations).

5 Sensitivity analyses to test for robustness of conclusions

Table 13: Cause-specific death

Population	Identical to primary analysis of primary outcome
Observation period	From: Enrolment visit or 24 hours after birth, whichever comes last To: 60 days of life Censoring, first of:

	
 - Visit by the BHP - 60 days - Death due to accident - Date of registering first non-trial vaccine given after enrolment - Migration (migration out of the study area as per HDSS definition)
Time scale	Age
Failure definition	Death due to: Malaria, Respiratory Infection, Sepsis, Gastrointestinal disease, Other
Statistical tool	Cox proportional hazards model
Stratification	We will employ models that allow for different baseline hazards according to sex, region and pre-study mortality level
Clustering	We will use robust standard errors to account for clustering within village cluster
Outline stata code For analysis: For model checking:	<pre>stset outdate, f(event==1&cause==X) enter (max(dob+1, date_enrol) /// exit (min (dnasc+60, date_mobileteam) origin(dob) stcox random, strata(sex reg prmorlev) vce(cl regam) estat phtest, detail† stphplot, strata(random) adj(sex reg prmorlev) stcox random, strata(sex reg prmorlev) vce(cl regam) tvc(random) texp(_t) *reg=region, prmorlev=pre-study mortality level, regam=village cluster</pre>

† If the proportional hazards assumption is not fulfilled we will still report the marginal hazard ratio but it will be supplemented by hazard ratios for two-three categorized time periods.

In sensitivity analyses, we will furthermore, assess whether the conclusions are robust to the following:

- Censoring follow-up at general health intervention campaigns (e.g. OPV campaigns)
- Altering the population to using an intention-to-treat approach, including all children, who had a home visit by a study nurse (i.e., including children who did not receive assigned treatment, children who were not enrolled because they were moribund, or who did not accept to participate).

- Altering the outcome from non-accidental mortality to all-cause mortality including also deaths due to accidents.
- For the non-accident hospitalisations, we will perform the analyses allowing for repeated hospitalisations. A child will return to the at-risk population the day after discharge from the hospital.

References

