## 1.2 Non-specific effects of BCG

Several observational studies in Africa and other high-mortality areas show that BCG is associated with better child survival, which cannot be explained by prevention of tuberculosis (TB).

WHO recommends BCG vaccine at birth to normal-birth-weight children (NBW) in low-income

countries to prevent TB. For low-birth-weight children (LBW;<2500g) BCG vaccination is often delayed because these children are assumed to be immunologically immature, and therefore they are typically only vaccinated when they have reached 2500g. However, in two RCTs in Guinea-Bissau, BCG-at-birth reduced neonatal mortality in LBW children by 48% (95%CI: 18-67%). TB is very rare in early childhood and these strong beneficial effects can therefore not be ascribed to prevention of TB. Rather the effect is due to a beneficial training of the immune system, preventing or ameliorating other infections, which cause neonatal and childhood death. The effect of BCG-at-birth on neonatal mortality was seen already during the first three days post-vaccination, the reduction in mortality being 58% (8-81%). This rapid effect suggests that the effect is due to changes in the innate immune system rather than the adaptive immune system.

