### 5.7 Statistical analyses

All children registered during pregnancy will enter the study when they are visited at home or 24 hours after birth, whichever comes last, thereby excluding deaths and hospital admissions on the day of birth.

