Appendix 1: General analysis principles

1 Participant population

All main analyses will be completed in a per-protocol (PP) population of all BCG-unvaccinated children, who received a home visit within 72 hours after birth, and who received the assigned treatment. The primary analysis and hence the main conclusion of the trial will be based on the PP analysis. Unless explicitly stated all analyses will be PP.

Since the cluster-size varies, data will be analysed on individual level data. All statistical tests will be 2-tailed and $p \leq 0.05$ considered statistically significant for analyses involving the primary outcome.

2 Unadjusted and adjusted analyses

Both unadjusted analyses and analyses adjusted for place of delivery will be reported. Conclusions will be based on the unadjusted analyses.

3 Multiple testing

P-values will not be corrected for multiple testing. Secondary outcomes are tested to observe if the pattern is similar across other health outcomes. Consequently, $p \leq 0.05$ will not be employed as a threshold for statistical significance for secondary outcomes. For the sensitivity analyses, we will not consider statistical significance, but rather robustness of the conclusions across different definitions of outcomes and co-variates.

4 Missing data

All analyses will be complete-case analyses.

5 Proportional hazards

To test the proportional hazards assumption, a required assumption of the Cox regression, we will perform formal significance tests based on Schoenfeld residuals. In addition, we will assess proportionality by allowing the hazard ratio to interact with the underlying timescale to identify a possible time trend. Finally, we will assess proportionality graphically via log-log survival curves.

Significance tests based on Schoenfeld residuals will be performed via the stata command *estat phtest, detail* leading to both a global test and a test for each covariate, the latter being relevant only when we study effect modifications. Presentation of log-log survival curves will be undertaken via *stphplot*. Finally, possible interactions between hazard ratios and the underlying time scale will be

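### On whole dates, the outline stset line drops events on the entry date, some of which the stated observation period counts

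*SAP*

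**What the plan says.** Table 2 in SAP Appendix 2 defines the start of observation as a clock-time rule: "From: Enrolment visit or 24 hours after birth, whichever comes last". Protocol section 5.7 gives the same rule and explains its effect as "thereby excluding deaths and hospital admissions on the day of birth".

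The outline code in Table 2 sets entry with "enter (max(dob+1, date_enrol" and continues "exit (min (dnasc+60, date_mobileteam) origin(dob". The entry and exit lines recur for hospital admission (Table 7), severe morbidity (Table 8) and cause-specific death (Table 13). Only the failure indicator changes.

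The per-protocol population is children "who received a home visit within 72 hours after birth, and who received the assigned treatment", so the entry date lies roughly between one and three days after the date of birth. Table 2 also excludes children judged at the visit to be unlikely to survive the next 24 hours. Neither document says how an event on the entry date is handled, and neither mentions recorded clock times for birth, visit or death.

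**The concern.** In Stata the risk interval opens just after entry and closes at exit. When both carry the same date, the child contributes no time, stset drops the record, and the death is not counted as a failure. The written observation period has no such gap: it opens at the visit, or at 24 hours of age if that is later.

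The affected date lies in the period that matters most to the trial's rationale. Protocol section 1.2 reports that the effect of BCG at birth "was seen already during the first three days post-vaccination", and section 2 puts about 75% of neonatal deaths in the first week. Section 5.5.1 already concedes that mortality may not give a conclusive result. If hazards prove non-proportional, Appendix 1 promises hazard ratios by time period, and an estimate for the earliest period would lose the largest share of its events.

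Two further places show why a rule is needed. Table 7 counts a child who reaches hospital and dies within the first day, so the plan means to count very rapid events. The intention-to-treat analysis brings moribund children back in. No separate stset line is given for it, so reusing this one would remove those who die on the entry date.

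**Working it through.** **Plan's own figure.** The documents give no count of entry-date events and no mortality proportion. The only related figure is the total of 6666 children in Protocol section 5.3, set for the composite outcome. A two-sided 5% test of two proportions with 80% power and no continuity correction, for 2.4% against 2.4% × 0.60 × 0.92 = 1.325%, gives 2481 per arm. Then 2 × 2481 × 1.35 = 6699, within 0.5% of 6666. This is used below only to scale the loss in power.

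**Which records are dropped.** Take the date of birth as day 0 and use whole dates. Entry = max(1, enrolment day), and a record is kept only if exit day > entry day.

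| Enrolled | Died | Entry | Code | Written observation period |
|---|---|---|---|---|
| day 0 or 1 | day 1, before 24 hours of age | 1 | dropped | not counted |
| day 0 or 1 | day 1, after the visit and after 24 hours | 1 | dropped | counted |
| day 2 | day 2, after the visit | 2 | dropped | counted |
| day 3 | day 3, after the visit | 3 | dropped | counted |
| any | at least one date after entry | – | kept | counted |

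Code and text disagree in rows 2 to 4. For deaths the order of events is not in doubt, since an enrolled child was alive at the visit. An admission on the entry date could have come before the visit.

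**Size of the loss.** The age pattern of deaths is an assumption. Let the cumulative share of 60-day deaths by age a (in days) be F(a) = (a/60)^b.

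- Steep end: b is chosen so that 75% of deaths in the first 28 days fall in week 1. b = ln(0.75)/ln(7/28) = 0.2075.
- Flat end: b = 1, a constant rate.

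Hand check for a visit at 36 hours of age. With birth hour uniform over the day, the time left on the entry date averages half a day. The approximate share of eligible deaths lost is [F(2.0) − F(1.5)] / [1 − F(1.5)].

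- b = 0.2075: (0.4937 − 0.4651) / (1 − 0.4651) = 5.3%. For week 1: 0.0286 / (0.6403 − 0.4651) = 16.3%.
- b = 1: (0.0333 − 0.0250) / (1 − 0.0250) = 0.9%. For week 1: 0.5 / 5.5 = 9.1%.

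A simulation over uniform birth hours, mean ages at visit of 0.5, 1.0 and 1.5 days, and b from 0.2075 to 1 gives:

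- 0.8% to 6.2% of eligible deaths to day 60 lost;
- 8% to 17% of eligible first-week deaths lost;
- 57% to 78% of the lost deaths within 24 hours of the visit.

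The simulation applies no moribund exclusion, which would lower these losses in the per-protocol set. It also applies no early censoring at Bandim Health Project visits, which would raise the share.

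**Power.** Suppose the same share of all composite events were lost. This is an upper bound, because the simulation is for deaths. With 6666/1.35/2 effective children per arm and 2.4% against 1.325%, power is 0.798 with no loss, 0.794 with 1% lost and 0.773 with 6% lost.

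**The case against.** The code is labelled an outline and would not run as printed. Its brackets do not balance, enter and exit lack the time keyword, and the date of birth appears under two names. The variable outdate is not defined, although it must carry the censoring rules that the line does not show. Whole-day resolution is inferred. All of this stands, and it is why the point is conditional. It does not remove the point, because the line is the SAP's only indication of how entry-date events are treated, and run as intended it departs from the written observation period.

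A reader might infer that all deaths in the first days are lost, or that every dropped death was eligible. The documents support neither. One calendar date per child is affected. Day-1 deaths before 24 hours of age are excluded by the text too. The moribund exclusion is aimed at deaths within 24 hours of the visit, so it already removes some of the per-protocol cases.

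A reader might also infer a biased hazard ratio. The same rule applies in both arms and no direction is shown. Section 1.2 describes an effect over the first three days after vaccination; it does not claim one within hours.

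Finally, Protocol section 5.6 says that main outcome events will be reviewed individually. That review may expose a mismatch in counts, but it does not put dropped records back into the model.

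**Conclusion.** The point holds on the condition that the analysis variables are whole dates. The code then drops entry-date events, and the written observation period counts some of them. The loss is about 1% to 6% of eligible deaths to day 60 and about 8% to 17% of eligible first-week deaths. These figures rest on the assumed age pattern of death, the assumed visit ages and the absence of a moribund exclusion. At most, composite power falls from about 0.80 to between 0.77 and 0.79. The consequence is a modest loss of early events and precision, with no directional bias shown.

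It is tempting to state the loss as a number of deaths. The documents do not allow it: the 2.4% in section 5.3 covers deaths and hospitalisations together, and no mortality proportion is given.

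A second, smaller gap appears on the way. The 24-hour rule and the explanation in section 5.7 that it removes events on the day of birth differ for a child who dies on calendar day 1 before reaching 24 hours of age.

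**What to change.** 1. State the rule for events dated on the entry date, and reconcile the 24-hour wording with the day-of-birth wording.
2. Add part of a day, for example 0.5, to the exit date only for events on the entry date that are confirmed as after the visit and after 24 hours of age (or after the day of birth, if that is the wording chosen). Use clock times where they are recorded.
3. Leave all other event dates and the exit cap unchanged. Adding half a day to every event would admit day-1 deaths under 24 hours of age and admissions before the visit. It would also push events dated on the cap past it, so that they became censored.
4. For admissions, confirm that the event followed the visit.
5. Apply the rule in Tables 2, 7, 8 and 13 and in the intention-to-treat analysis. Check that the stset failure count equals the number of eligible events, and report entry-date deaths by arm.

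The cost is a few lines of code and individual review of a small number of events. No new data are needed unless clock times are wanted and were not recorded.
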